
Blinding. Participants cannot be blinded as to which group they are randomized. Laboratory technicians ascertaining the primary endpoint will be blinded as to arm assignment, and the research staff will also be blinded as above. The data analysis will be blinded as to group assignment by using a dummy variable for intervention vs. comparison until the analyses are completed.

TEXT MESSAGE-BASED INTERVENTION

While **all** households will receive the surveillance text messages, we will randomize households within each surveillance community to **additionally** receive educational text message about ways to decrease household

transmission (surveillance + education arm) vs. standard care (surveillance-only arm). We will then assess the impact of the educational text messages primarily on secondary attack rates of influenza within households.

The comparison arm will not receive any educational text messages, only the surveillance ones as above.

Message Generation. When an ILI/ARI is reported, research staff will log it into the text message application. If the household is in the surveillance + education arm, the system will automatically send one educational message to the household reporter a day for three days; if it is surveillance-only the system will not send a message. This allows research staff to remain blinded. Messages will be based on whether it is an adult or child who is the index case (Appendix). We have chosen three messages since after that most within-household transmission will have occurred. The household reporter will be instructed on enrollment that they are to read the text message to the household members. We have designed 4 sets of message to be used in order per household i.e. each household will start with set one (see Appendix for adult and child-specific sets of messages). The message will be targeted to be from the recruitment site (e.g. doctor's office, Head Start). We will track reports of undelivered messages; these are visible in the text message application.

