Intervention Message Design Including Cultural Sensitivity. We have designed sample sets of messages (see Appendix) based on the Health Belief Model that includes the CDC recommended information to decrease influenza and other respiratory pathogen transmission, the relevant literature, and the team's expertise in text messaging, influenza, disease transmission, health literacy and the community. As mentioned above, our team includes [name], an expert in cultural competency, who runs a health literacy program that has been federally funded, *Health Education and Adult Literacy*. Messages will include information that an

ill individual can pass the respiratory illness to their household members, that transmission can be harmful to household members, suggestions for behavior change, and the effectiveness of behavior change (Figure 4). Some of the messages will be interactive since in our previous vaccination-related intervention, we found that including one interactive message increased the intervention effect.^{20,41} While keeping within the 160-character count, we designed messages to be no more than a 5th grade reading level according to the Flesch-Kincaid

Figure 4: Examples of Potential Set Text Messages for a Sick Adult

Text Message Examples	Health Belief Model Factor
Audubon Clinic: People with flu and other viruses could get others sick up to 5-7 days after they themselves get sick. It could be much worse than a bad cold!	Perceived susceptibility of contracting the disease Perceived severity of the disease.
Audubon Clinic: Avoid others getting sick in your house. Wash hands often with soap and water or use an alcohol-based hand sanitizer.	Perceived barriers to adoption of the behavior
Audubon Clinic: Have a household talk about how to prevent spreading the flu and other viruses. It has been shown to work!	Perceived effectiveness of the behavior

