All analyses will be based on randomized arm assignment (intention-to-treat). An ill person will be considered an ILI/ARI index case for a household if, at the onset of illness, no one else in the household had been symptomatic within the previous 5 days.²⁹ Non-index household members will be defined as secondary cases if they are confirmed by RT-PCR as influenza-positive on day 3 or day 5 swab (symptomatic or asymptomatic).¹⁶ Five days was selected based on our previous studies and the influenza incubation period.²⁹ The secondary attack rate will be defined as the number of secondary cases of laboratory-confirmed influenza (both symptomatic and asymptomatic) divided by the number of household members minus one (the index case). Secondary attack rates will be compared between the arms - surveillance plus education vs. surveillance-only - using chi square tests and a generalized linear mixed model (logistic regression for binary response, mixed model for clustering within a household). We will assess other co-variates in the models including for the index patient and household contacts: age, sex, vaccination status including vaccine type, antiviral use (treatment or prophylaxis), previous illness episodes reported for the household, influenza season and years in study.

Secondarily, we will assess the intervention's impact on additional outcomes using the same analyses as above: defining secondary cases based on (1) ILI-criteria (fever, cough, headache, sore throat, or myalgia) within 5 days of illness of index case; (2) ARI criteria (≥ 2 of a) rhinorrhea/nasal congestion; b) sore throat; c) cough; d) fever/feverishness; e) myalgia); (3) any laboratory-confirmed pathogen that is the same as the index case including non-influenza pathogens. An additional set of secondary outcome measures will be to assess the secondary attack rate at the household (cluster) level defined as the percentage of households with at least one secondary case as defined in the analyses above.

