We will minimize the amount of missing household-time due to attrition by replacing households who are lost to follow up that year if there are ≥ 2 months left in the influenza season or the next year if there are < 2 months left. We recognize that reasons for dropping out may be correlated with the outcome; this cannot be tested directly in the data. We will therefore add an indicator in the models for replacement households and test for association. Also, we will perform sensitivity analyses analyzing only the originally randomized study sample (exclude replacement households). Weak or no association for the indicator variable and consistency in the association between random arm assignment and outcome between the whole sample and the sample excluding replacement households will be interpreted as evidence supporting use of the entire sample. We will also conduct sensitivity analyses in which we assign the outcome of secondary transmission in the replacement sample to infection to make it a worse case scenario, with the caveat that this will only be possible if the dropout rate is low. If dropout rate is high, the range of possible estimation is too large.

Missing Data. We will document missing data and classify by variable and arm. We will then assess any relationships between missingness and covariates such as demographics or arm. Missing data due to attrition was discussed above. Missing data due to other reasons will also need to be taken into account. The main concern related to the primary outcome will be household contacts who do not obtain swabs. We will impute these data using multiple imputation following the methodology of Rubin.⁸³ A more conservative approach would be to consider all household members missing swab data to be failures⁸ (to have been infected with influenza), but this is highly unlikely to be an accurate reflection of the true case, unduly weights drop-outs in the analysis, and is not the currently preferred approach to missing data.^{84,85} Covariate data may also be missing. We will also impute these variables using multiple imputation following the methodology of Rubin.⁸³

Exploratory Aim: To compare the yield of text message ILI/ARI surveillance among subgroups in a diverse, community sample

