We will use Pearson chi square to assess relationship between text message response rates and community, reporter's race/ethnicity, insurance and education. This will be defined as number of responses received per message sent. If more than one variable is significantly related to reporting rates ($p<0.1$), we will develop multivariable logistic models to assess this relationship. We will also assess response rates by arm.

SAMPLE SIZE AND POWER

We have based our sample size on the primary outcome. With 200 households per arm and an average of 3.8 persons/household, we will have 88% power to detect a decrease in secondary attack rates of laboratory-confirmed influenza from 12% (surveillance-only) to 5% (surveillance + education), based on type I error of 5% and an intracluster correlation coefficient of 0.29. The intracluster correlation, expected transmission rates for the surveillance-only arm, and effect size are derived from the paper by Cowling *et al.*, reporting a reduction from 12% to 5% between the hand hygiene and usual care arms in SAR when a non-text message based behavioral intervention was started at ≤ 36 hours of illness onset in the index case using laboratory-confirmed influenza as an outcome.¹⁶ In the MoSAIC study, secondary attack rates for laboratory-confirmed influenza have been 16.6% therefore an expected rate of 12% in the surveillance-only arm is conservative. We will also be powered for our secondary outcome; we will have 91% power to detect a decrease in symptomatic ILI/ARI from 23% to 11%.¹⁶ If we lose 80 households (20%) per season, we will still have at least 80% power to detect the decreases in both the primary and secondary outcome as above, even without household replacement.

POTENTIAL CHALLENGES AND SOLUTIONS Table 3

Challenge	Solution
1. Recruitment and retention	In our previous community studies retention was excellent. In our MoSAIC study, 75.9% of households recruited in year 1 were still in the study in year 3.
2. Non-representative sample	Since eligibility criteria include ≥ 3 members and ≥ 1 child, the sample will not be fully representative of the communities. However, the benefits of these inclusion criteria include higher likelihood of infection and transmission.
3. Reporting bias	3x/a week texting will decrease recall bias. We have shown under- and over-reporting to be low and confirmed the validity of household symptom self-reports.

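### Neither the chi-square test nor the household mixed model is named as primary; uncorrected for clustering, the contact-level chi-square would have a type I error of about 11-12%, not 5%

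*Combined protocol and SAP*

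**What the plan says.** The Statistical Plan (Aim) defines the secondary attack rate per contact: secondary cases over household members other than the index case. Arms are compared "using chi square tests and a generalized linear mixed model (logistic regression for binary response, mixed model for clustering within a household". The two methods are joined by 'and', and no sentence in the document says which one decides the trial. The clustering purpose is attached to the mixed model only.

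On covariates the plan says "We will assess other co-variates in the models including for the index patient and household contacts". The list includes "antiviral use (treatment or prophylaxis), previous illness episodes reported for the household, influenza season and years in study". It is open-ended, has no retention rule, and does not say whether the deciding model is adjusted. For replacement households it adds: "We will therefore add an indicator in the models for replacement households and test for association". The further outcomes are handled the same way: "impact on additional outcomes using the same analyses as above". They include household-level versions (the percentage of households with at least one secondary case).

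Sample Size and Power states that the calculation is "based on type I error of 5% and an intracluster correlation coefficient of 0.29".

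On timing, households are randomised at enrolment (Randomization Procedures). After a reported illness in the education arm, "the system will automatically send one educational message to the household reporter a day for three days" (Message Generation). Contacts are swabbed on days 3 and 5. Antiviral use is asked in a call on day 10 (Symptom Reports). Neither antiviral use nor previous illness episodes is in the list of data gathered at enrolment (Survey Tools).

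**The concern.** Contacts in one household share an index case, so their outcomes are correlated. A chi-square that counts each contact as independent understates the variance of the arm difference and rejects a true null too often. With two methods stated and no order between them, a reader cannot tell from the text which p-value is the trial result, and the two can disagree. The same choice carries over to the contact-level secondary outcomes.

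The covariates raise a second, smaller issue. Antiviral use is recorded after the messages and the swabs. The messages could affect it indirectly through perceived severity and care-seeking (one sample reads "It could be much worse than a bad cold"), although the sample messages shown do not mention antivirals. A contact's treatment may also follow the infection being counted. Previous episodes can accrue on study, because households may have repeat episodes and may continue across seasons. Conditioning on either gives an arm effect that is no longer protected by randomisation.

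**Working it through.** **Inputs.** 200 households per arm, 3.8 persons per household, ICC 0.29, alpha 5% (taken as two-sided, since sidedness is not stated), 12% vs 5%, power 88% (Sample Size and Power). Contacts per household are 3.8 - 1 = 2.8 (Statistical Plan), so 200 × 2.8 = 560 contacts per arm.

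**1. The plan's own power.** Two-proportion formula, pooled variance under the null, effective n = contacts / design effect.
- Design effect 1 + (3.8 - 1) × 0.29 = 1.812: n = 560 / 1.812 = 309.1, power 0.879. This matches the stated 88%. With 160 households per arm it gives 0.799, against the stated minimum of 80%.
- Design effect 1 + (2.8 - 1) × 0.29 = 1.522: n = 367.9, power 0.927.
- No clustering: n = 560, power 0.988.

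Of the variants tried, only the first comes within two points of 88%. It uses 3.8 persons in the design effect but 2.8 contacts in n, which is conservative. The sample size therefore presumes a clustered analysis.

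**2. Type I error of an uncorrected contact-level chi-square.** Formula: 2 × (1 - Φ(1.96 / √DE)), with DE = 1 + (m - 1) × ICC.

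| Contacts m | ICC | DE | Type I error |
|---|---|---|---|
| 2.8 | 0.29 | 1.522 | 11.2% |
| 2.8 | 0.10 (assumed) | 1.180 | 7.1% |
| 2.8 | 0.05 (assumed) | 1.090 | 6.0% |
| 5.6 (two episodes, same ICC across both; upper bound) | 0.29 | 2.334 | 20.0% |

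**3. Unequal household sizes.** Assume 2/3/4/5 contacts with shares 47/32/15/6%. The mean is 2.8 and the mean square is 8.66, so DE = 1 + (8.66 / 2.8 - 1) × 0.29 = 1.607 and the error is 12.2%. Beta-binomial simulation (ICC 0.29, 12% in both arms, 10,000 null trials each at 200, 100 and 60 households per arm) gives 12.0%, 12.4% and 12.3% for the chi-square. A cluster-adjusted comparison of proportions gives 5.0-5.4%. The inflation hardly depends on how many households contribute.

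**4. Chi-square against mixed model on the same trials.** In a separate 3,000 null trials at 200 households per arm, the chi-square rejected in 13.4% and the random-intercept logistic model in 5.2%. In 8.2% only the chi-square was significant. With a standard error of √(0.134 × 0.866 / 3,000) = 0.6 points, 13.4% lies about two standard errors above 12.2%.

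**5. Household-level secondary outcomes.** With one episode per household there is one observation per cluster, so within-household correlation does not invalidate a chi-square there.

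**6. Antiviral adjustment.** The documents give no rates, so this is illustration only. Assume a control attack rate of 12%, an antiviral odds ratio of 0.5, and an arm odds ratio given antiviral use of 0.6 or 0.386. The share of the total log odds ratio kept after adjustment is:
- use 10% control vs 20% education: 90-95%;
- equal use: about 100%;
- use 10% control vs 5% education: 103-106%.

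Worked case: with 0.6 and 10% vs 20% use, the education rate is 7.19% and the total odds ratio 0.568, so ln 0.6 / ln 0.568 = 0.90. No figure can be given for previous episodes.

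**The case against.** The plan leans towards the mixed model. That model's stated purpose is household clustering, the trial is sized with an ICC, and covariates and the replacement indicator go into models, which a plain chi-square cannot carry. The natural reading is a simple chi-square beside an inferential mixed model. This stands as evidence of intent, but it does not replace a sentence naming the primary analysis. Intention-to-treat settles who is analysed, and dummy-coded arms hide which arm is which; neither settles which test counts.

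A reader might infer that an uncorrected chi-square will decide the trial. No text says so. A reader might also put the error at nearly three times nominal by using the design effect of 1.812 (14.5%). That treats 3.8 persons as 3.8 contacts, whereas the plan's denominator excludes the index case.

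The ICC is taken from a cited trial, and at lower values the inflation is small. On covariates, the plan says only that they will be assessed, which may mean supplementary models. That previous episodes are on-study events is an inference from the enrolment list.

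Finally, a richly specified mixed model with about 2.8 binary contacts per household may not converge. This stands, and the fix has to provide for it.

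**Conclusion.** The concern holds as a gap in specification: two methods are stated, neither is primary, and one of them gives a wrong p-value at the plan's own ICC unless it is corrected. The size is a type I error of about 11-12% instead of 5%. It rests on ICC 0.29, 2.8 contacts per household, one episode per household and a two-sided test. It falls to about 6-7% at an ICC of 0.05-0.10 and rises with repeat episodes. It does not extend to the household-level secondary outcomes with one episode per household.

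The covariate point is secondary. Antiviral use is clearly recorded after randomisation and previous episodes probably arise after it, so neither belongs in the primary model. A reader might infer that the primary estimate will be materially biased. The documents do not support that: they do not commit these covariates to the primary model and give no antiviral rates by arm. The size and direction of any shift are unknown and likely modest.

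**What to change.** In the SAP:

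- Name the household-clustered mixed model as the single primary analysis. Include arm, a household random effect, the randomisation strata, influenza season, age and sex. The strata are community and sampling site (pooled where small), once Specific Aims (community only) and Randomization Procedures (community and sampling site) are reconciled.
- Pre-state a simpler clustered fallback in case it does not converge, for example GEE or a cluster-robust comparison of proportions.
- Make the contact-level chi-square descriptive or cluster-adjusted, and apply the same rule to the contact-level secondary outcomes.
- Report antiviral use and on-study previous episodes by arm. Label any model containing them, or the replacement-household indicator, as supportive.

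The cost is SAP wording and a few extra terms. At the design rates, with one episode per household, about 560 × 0.12 + 560 × 0.05 = 67 + 28 = 95 secondary cases are expected. Hence the short covariate list, the pooling of small sites and the fallback.

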We will enroll and randomize 400 households (n=~1500 individuals) with ≥ 1 child recruited from four contiguous communities in New York City 1:1, stratified by community, to receive surveillance-only vs. surveillance plus text message educational intervention. We will have 88% power to detect a decrease in influenza SAR from 12% to 5%. These percentages are derived from the paper by Cowling *et al.*, reporting a reduction from 12% to 5% between hand hygiene and usual care arms in SAR for influenza when a non-text message-based behavioral intervention was started ≤ 36 hours of index illness onset.¹⁶ For surveillance, households in both arms will receive text messages 3x/week during each influenza season (Nov-Mar) and report household members with ILI/ARI symptoms. For those in the educational intervention arm, when an ILI/ARI is reported, educational text messages will be sent targeted to decrease household transmission.

Both arms will obtain one self-swab of the index case, and self-swabs of all other household members on days 3 and 5 from index onset.^{7,10,13,24} Swabs will be returned via postage-paid envelope and analyzed using an FDA-approved reverse-transcriptase multiplex PCR assay to identify influenza, including sub-types, as well as other viral respiratory pathogens, e.g., parainfluenza etc. We will also collect symptom reports from all household members. The primary outcome will be SAR of laboratory-confirmed influenza. Secondarily, we will assess SAR based on ILI/ARI symptoms, and of non-influenza viruses. Response rates will be compared between arms and by demographic factors (age, education, race/ethnicity). Trial results could provide support for text-based strategies to reduce influenza transmission.

B. RESEARCH STRATEGY

SIGNIFICANCE

Impact of Influenza: Influenza infection results in an estimated 31 million outpatient visits, 55,000 to 974,200 hospitalizations (2014-15 estimate: 974,206), and 3000 to 49,000 deaths (2014-15 estimate: 49,006) annually.¹⁻³ The burden of influenza also includes high cost from direct medical expenses, days lost from work or school,²⁵ and inappropriate use of antibiotics.²⁶ Children and adolescents 6 months-18 years old are at increased risk of influenza morbidity and mortality, and influenza is one of the most common causes of hospitalization for the pediatric population.¹ School-aged children and adolescents also serve as an important reservoir, transmitting influenza to household members.^{1,27}

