Annual home visits will be made to all enrolled households wanting to continue the next respiratory season to facilitate retention and participation, answer questions, ensure contact information remains correct, update household composition changes, and provide swab kits. Households that continue to meet eligibility criteria (Table 2) may continue into the next respiratory season. Households will receive \$50 on enrollment and \$25 at this re-enrollment visit; this will aid with enrollment and retention. Participants will also receive compensation for reporting and returning self-swabs as outlined below. If a household no longer meets eligibility criteria during a season or if are lost to follow-up, we will replace households in the same season if there are ≥2 months left in the influenza season or the next year if there are <2months left. Households that leave the study will be replaced using the same procedures as for the baseline sample using 1:1 randomization. Based on previous studies, we expect 10-20% of households to be replaced yearly.^{18,29,67}

TEXT MESSAGE SURVEILLANCE FOR ILI/ARI

Both arms (surveillance + education vs. surveillance-only) will receive text messages to perform surveillance of household members for ILI/ARI. The surveillance period will run November through March each year. We have chosen that period since for the past 9 years (with the exception of the 2009 influenza A H1N1 pandemic) the earliest onset of influenza in these communities has been in November and we have seen the vast majority of influenza cases by March.^{18,68} If there are unusual influenza patterns, we will be able to start sample collection earlier or end it later. During the surveillance period, each household reporter in all households will automatically receive text messages three-times a week from the text messaging system (a.k.a. *research staff-generated messages*) asking if any household member has symptoms included in the study case definitions for ILI/ARI and asked to respond whether or not anyone is ill (Figure 3). Households will be texted on a Monday, Wednesday and Friday schedule to optimize days between reporting. We have chosen this schedule so that intervention can start within 36 hours of onset. Messages will be sent in English or Spanish based on the

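### The worst-case attrition analysis assigns infection to the replacement households, not to those that left, and gives no rule by arm, so it does not bound the arm comparison

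*Combined protocol and SAP*

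**What the plan says.** The attrition paragraph of the Statistical Plan (under the main Aim) accepts that "reasons for dropping out may be correlated with the outcome; this cannot be tested directly in the data". It plans three checks: a model indicator for replacement households, a repeat analysis restricted to the originally randomized households, and a scenario in which "we assign the outcome of secondary transmission in the replacement sample to infection to make it a worse case scenario". The scenario comes "with the caveat that this will only be possible if the dropout rate is low", and the paragraph closes: "If dropout rate is high, the range of possible estimation is too large". No threshold for low or high dropout is given, and no arm is named.

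Under Randomization Procedures, "Households that leave the study will be replaced using the same procedures as for the baseline sample using 1:1 randomization". The Specific Aims state that both arms provide "self-swabs of all other household members on days 3 and 5 from index onset", so replacement households generate their own outcome data.

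The Missing Data paragraph describes multiple imputation for contacts who did not provide swabs and for covariates. It treats attrition as already dealt with in the preceding paragraph.

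**The concern.** The scenario is meant to answer one question: could outcomes that were never seen, in households that left, change the comparison between arms? As written, it alters a different set of households. A replacement household's outcome is not missing, and because it is randomized afresh it need not be in the arm of the household it replaces. Setting it to infected discards data and says nothing about the household that left.

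The other two checks do not fill the gap. The indicator and the originals-only analysis use observed outcomes only, and the imputation is not described as covering departed households. This sentence is therefore the only planned scenario analysis for outcome-related dropout. At stake is what a reader may conclude from it: a result labelled worst case would be taken as a bound on the treatment comparison when it is not one.

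**Working it through.** The plan gives no numerical result for this analysis, so there is no figure to reproduce. The stated power does not enter.

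**Inputs**
- Planned attack rates: 12% surveillance-only, 5% surveillance plus education (Sample Size and Power). Difference, surveillance-only minus education: 7 points.
- Highest laboratory-confirmed household attack rate cited: 19% (Specific Aims; Significance). The investigators' earlier surveillance study: 16.6% (Sample Size and Power).
- d: share of analysed contacts affected, taken as equal in the two arms. This is an assumption, shown at 10% and 20%; the documents do not give it.
- Also assumed: planning rates hold in all other contacts, household sizes are equal, and each household contributes one influenza-index episode.

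**1. Infection assigned in both arms.** The algebra is the same whether d is the share in replacement households (literal reading) or in departed households (charitable reading).

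Difference = [(1-d) x 0.12 + d] - [(1-d) x 0.05 + d] = (1-d) x 0.07
- d = 10%: 20.8% - 14.5% = 6.3 points
- d = 20%: 29.6% - 24.0% = 5.6 points

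The added d cancels. With equal shares the result is a single value that keeps the sign of the planned effect.

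**2. Infection assigned to departed households by arm**

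Least favourable to education (education infected, surveillance-only not): (1-d) x 0.12 - [(1-d) x 0.05 + d]
- d = 10%: 10.8% - 14.5% = -3.7 points
- d = 20%: 9.6% - 24.0% = -14.4 points

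Most favourable (the reverse): [(1-d) x 0.12 + d] - (1-d) x 0.05
- d = 10%: 20.8% - 4.5% = +16.3 points
- d = 20%: 29.6% - 4.0% = +25.6 points

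**3. Tipping points.** If departed surveillance-only households have attack rate c, the arms are equal when departed education households have x = c + (1-d) x 0.07 / d.
- c = 12%: x = 75% (d = 10%) or 40% (d = 20%)
- c = 0%: x = 63% (d = 10%) or 28% (d = 20%)

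**4. Check against the protocol's own range.** Put departed education households at 19% and departed surveillance-only households at 0%.
- d = 10%: 10.8% vs 0.9 x 5% + 0.1 x 19% = 6.4%
- d = 20%: 9.6% vs 0.8 x 5% + 0.2 x 19% = 7.8%

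Education remains ahead by 4.4 and 1.8 points.

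**The case against.** The strongest reply is that the sentence is loosely worded rather than wrong. It is conditional on the dropout rate and followed by a remark about a range of estimates, which fits bounds on the departed households better than a rule about their replacements. That is a fair reading, and it may be what was intended. It does not supply the missing assignment by arm, and without one there is no range to report.

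A second reply is that extreme bounds are uninformative. The Missing Data paragraph says of treating every contact without swabs as infected that "this is highly unlikely to be an accurate reflection of the true case", and the width of the bounds at 20% bears this out. This stands, and it is a reason to add intermediate values. It also limits the claim. A reader might infer that the plan would hide a real reversal, but every tipping point in the working exceeds the 19% cited, and the arms do not cross at that rate. The reservation is that this uses the planned effect; a smaller observed effect would tip sooner.

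Other stronger inferences lack support:
- The protocol states that "we expect 10-20% of households to be replaced yearly". It is tempting to read that as d and conclude that the adverse bound would cross zero in practice. The two are not like for like. Replacement also covers households that cease to be eligible, a household may have contributed episodes before leaving, and its departure matters here only if an influenza-index episode was missed.
- One might suppose that the literal and charitable readings would give opposite answers. That needs dropout to differ between arms, and the documents give no attrition by arm.
- One might say that attrition by arm is ignored. The Missing Data paragraph already plans to classify missing data by variable and arm.

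**Conclusion.** The point holds for a sensitivity analysis that runs only if dropout is low. As written, it changes the wrong households. Read charitably, it lacks the arm rule that would make it a bound. Infection in both arms with equal shares moves 7 points only to 6.3 or 5.6, against arm-specific bounds of -3.7 to +16.3 and -14.4 to +25.6 at d = 10% and 20%. The sizes rest on the planning rates, equal shares by arm and one episode per household. The true d is unknown and probably below the yearly replacement rate.

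A reader might infer that the trial's main result is compromised. It is not: the primary analysis does not use this scenario. The plan's stated grounds for relying on the whole sample are the replacement indicator and the originals-only comparison. The correction is worth making because this is the only planned scenario analysis for a risk that the plan itself says it cannot test.

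**What to change.** Amend the attrition paragraph of the Statistical Plan to:
- keep replacement households' observed outcomes in every analysis;
- apply the scenario to the departed households' missing household-time, by randomized arm: education infected and surveillance-only not, then the reverse;
- add intermediate tipping-point values, and report the attack rate at which the conclusion changes beside the protocol's figure of up to 19%;
- state how the departed households' expected influenza-index episodes and contacts are counted, since the attack rate is defined only after an index case.

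The cost is revised wording and modest extra programming, with no new data. The downside is a possibly less favourable robustness statement.
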